1. OBJECTIVES

1.1 Primary Objectives

1.1.1 Rate of grade 3-5 cisplatin-related adverse events occurring within 90 days of initiation of concurrent radiation and chemotherapy including:

- nausea/vomiting
- ototoxicity
- nephrotoxicity
- neutropenia
- thrombocytopenia

1.1.2 Hypothesis: Patients with locally advanced non-nasopharyngeal SCCHN treated with weekly cisplatin (40 mg/m² weekly for 7 doses) with radiation (RT) will have fewer cisplatin-related acute toxicities as compared to those receiving every three-week cisplatin (100 mg/m² for 3 doses) with radiation in the following cohorts:

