7.2 Adverse Event Characteristics

- **CTCAE term (AE description) and grade:** The descriptions and grading scales found in the revised NCI Common Terminology Criteria for Adverse Events (CTCAE) version 4.0 will be utilized for AE reporting. All appropriate treatment areas should have access to a copy of the CTCAE version 4.0. A copy of the CTCAE version 4.0 can be downloaded from the CTEP web site:
http://ctep.cancer.gov/protocolDevelopment/electronic_applications/ctc.htm.
- **For expedited reporting purposes only:**
 - AEs for the agent(s) that are listed above should be reported only if the adverse event varies in nature, intensity or frequency from the expected toxicity information which is provided.
 - Other AEs for the protocol that do not require expedited reporting are outlined in the next section (Expedited Adverse Event Reporting) under the sub-heading of Protocol-Specific Expedited Adverse Event Reporting Exclusions.
- **Attribution of the AE:**
 - Definite – The AE is *clearly related* to the study treatment.
 - Probable – The AE is *likely related* to the study treatment.
 - Possible – The AE *may be related* to the study treatment.
 - Unlikely – The AE is *doubtfully related* to the study treatment.
 - Unrelated – The AE is *clearly NOT related* to the study treatment.

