13. STATISTICAL CONSIDERATIONS

13.1 Study Design/Endpoints

This is a 1:1 randomized, unblinded phase II trial of radiation with cisplatin weekly versus every three weeks for patients with locally advanced non-nasopharyngeal SCCHN. The primary endpoint is cisplatin-related acute toxicities (within the first 90 days after the start of radiation). These include all grade 3-5 events of nausea/vomiting, ototoxicity, nephrotoxicity, and neutropenia and thrombocytopenia. Secondary objectives include clinical outcomes (2-year local control rates, OS, PFS, response), additional toxicity outcomes (rates of dysphagia, dry mouth, and skin, other acute and late events according to CTCAE), correlates (oxidative stress markers), and quality of life outcomes (FACTHN, FACTCOG).

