13.4 Analysis Plan

Following study completion, the percentage of subjects experiencing cisplatin-related actual toxicities in each group will be estimated along with exact 95% binomial confidence intervals. A Fisher's exact test will also be employed to test for differences between toxicity rates.

For all toxicity outcomes, incidence tables will be generated to summarize incidence of patients reporting at least one episode of each adverse event, incidence of adverse events causing withdrawals and incidence of serious adverse events. Listing of adverse events by patients will include the time to onset, the duration of each event, the severity of each event, and the relationship of the event to study therapy, whether it was a serious event, and whether it caused withdrawal.

All correlative and secondary endpoints are exploratory in nature and will be primarily descriptive; however, response and 2-year local control rates will be estimated with corresponding 95% confidence intervals and assessed for differences using Fisher's exact tests. PFS and OS will be displayed using Kaplan-Meier curves with estimated median times, and differences will be assessed using log rank tests. Repeated measures mixed models will be utilized to assess for differences in quality of life and correlative outcomes over time and between randomization groups.

In addition to those outlined above, subgroup analyses will also be run for each stratification cohort as numbers allow.

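### The protocol does not say whether cisplatin-related, in the primary endpoint, is a label for five event types or a case-by-case attribution filter; in an unblinded trial a filter could bias the comparison

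*Combined protocol and SAP*

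**What the plan says.** Three sections describe the primary endpoint.

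- Section 1.1.1: "Rate of grade 3-5 cisplatin-related adverse events occurring within 90 days" of the start of chemoradiation, followed by five event types.
- Section 13.1: "The primary endpoint is cisplatin-related acute toxicities (within the first 90 days after the start of radiation)". The next sentence reads: "These include all grade 3-5 events of nausea/vomiting, ototoxicity, nephrotoxicity, and neutropenia and thrombocytopenia".
- Section 13.4: "the percentage of subjects experiencing cisplatin-related actual toxicities in each group will be estimated along with exact 95% binomial confidence intervals", followed by a Fisher's exact test.

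Three other places bear on the meaning.

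- Sections 1.2.4 and 1.2.5, for secondary acute and late adverse events, state an attribution rule: possible, probable or definite relation to cisplatin or radiation. Section 1.1.1 has no such rule.
- Section 7.2, under "Attribution of the AE", defines a five-category scale. It is anchored to the study treatment as a whole and does not separate cisplatin from radiation.
- Section 13.1 describes the design: "This is a 1:1 randomized, unblinded phase II trial". Section 1.1.2 states the hypothesis that weekly dosing gives fewer cisplatin-related acute toxicities.

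**The concern.** An analyst working from this text could build either of two datasets. One counts every patient with a grade 3-5 event of the five types. The other counts only patients with such an event judged to be due to cisplatin. The two need not agree, and nothing fixes the choice before the data are seen.

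The second version would depend on judgment by staff who know the arm and the hypothesis. The cut-off would have to be invented, and so would a way to separate cisplatin from radiation, because 7.2 does not provide one. Some of the judgments are open to dispute: 7.1.1.1 notes that cranial irradiation may enhance ototoxicity, and 5.3.3 lists hearing loss among the less common long-term radiation effects. If weekly-arm events were attributed to cisplatin slightly less often, a difference would appear in the hypothesised direction without any true difference.

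The list itself is also not clearly closed. Sections 1.1.1 and 13.1 introduce it with forms of *include*, whereas 1.2.3 introduces its list of radiation effects as specific.

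**Working it through.** **Inputs from section 13.2.** Event rate 80% (every 3 weeks) and 50% (weekly); 36 patients per arm; Fisher's exact test; one-sided level 0.05; 10% loss to follow-up; 80 recruited.

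**Inputs assumed.** The share of patients with a listed event whose event is attributed to cisplatin. The documents give no such share.

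**Method.** Let X and Y be the numbers of patients counted as events in the 3-weekly and weekly arms. The one-sided Fisher p-value is p(x, y) = P(H ≥ x), with H hypergeometric given 72 patients, x + y events and 36 patients in the 3-weekly arm. The exact rejection probability is

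Σₓ Σᵧ Bin(x; 36, p₁) · Bin(y; 36, p₂) · 1[p(x, y) ≤ 0.05].

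**Step 1: the plan's own figure.** With p₁ = 0.80 and p₂ = 0.50 the power is 0.809, against the stated 80%. With 35 per arm it is 0.791. For loss to follow-up, 72 / (1 − 0.10) = 80. Both figures reproduce. With 0.80 in both arms the actual type I error is 0.027.

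**Step 2: a filter that differs between arms, no true difference.** Recorded rate = all-event rate × share attributed. The 3-weekly arm is fully attributed and the weekly arm is not. At the 80% rate the recorded weekly rates are 0.80 × 0.95 = 0.76, 0.80 × 0.90 = 0.72 and 0.80 × 0.85 = 0.68. At 50% they are 0.475, 0.45 and 0.425.

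| Share attributed, weekly arm | False-positive rate at 80% | False-positive rate at 50% |
|---|---|---|
| 100% | 2.7% | 3.8% |
| 95% | 6.6% | 5.9% |
| 90% | 13.2% | 8.9% |
| 85% | 22.8% | 12.7% |

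Full attribution in one arm is not needed. At the 80% rate, 95% against 90% gives 6.4%, and 90% against 80% gives 12.5%.

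In patients: 36 × 0.80 = 28.8 expected with an event in the weekly arm. Shares of 95%, 90% and 85% reclassify 28.8 × 0.05 = 1.4, 28.8 × 0.10 = 2.9 and 28.8 × 0.15 = 4.3 of them.

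**Step 3: a filter that is equal in both arms.** With no true difference at the 80% rate, the error is 2.8% at 95% in both arms, 2.9% at 90% and 3.3% at 80%. All are below 5%. For a true 80% against 50%, power falls:

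| Share attributed, both arms | Recorded rates | Power |
|---|---|---|
| 100% | 0.80 v 0.50 | 0.809 |
| 95% | 0.76 v 0.475 | 0.760 |
| 90% | 0.72 v 0.45 | 0.712 |
| 80% | 0.64 v 0.40 | 0.613 |

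This loss applies if 80% and 50% are all-event rates. Section 13.2 does not say whether the historical 80% is attributed or all-cause.

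**The case against.** A reader might infer that 1.1.1 and 13.4 already filter the endpoint by unblinded attribution, and that 13.1 contradicts them. The text does not support that. Neither 1.1.1 nor 13.4 contains an attribution step, an assessor or a cut-off; each uses only an adjective. Section 13.1 uses the same adjective before it lists the types, so it is not a clean contrast.

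There is a good case that no filter was meant. Where the protocol wants attribution it spells it out, in 1.2.4 and 1.2.5. Section 1.2.3 follows a similar adjective for radiation with named event types and no attribution grade. In 13.1 the second sentence reads naturally as explaining the first. No cisplatin-specific attribution is described in 7.2, and in 13.4 relationship to therapy is only an item in the adverse event listing.

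The error rates can also be challenged. The shares are assumed, and a patient drops out of the count only if every listed event is judged unrelated. The possible category in 7.2 needs only that the event may be related. A gap in the other direction would make the test conservative. Neutropenia and thrombocytopenia are laboratory-based and leave less room for opinion.

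All of this stands, and it makes the label reading reasonable. It does not settle the matter: no section says that attribution is disregarded, and the same objectives section uses relatedness as an attribution term.

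**Conclusion.** The primary endpoint is ambiguous on whether attribution counts, by whom it would be judged and at what cut-off. The documents do not show that a filter is planned, and they do not show that one is excluded.

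The risk is conditional. If attribution is applied and the weekly arm's share is 5 to 15 points lower, the one-sided error rises to between 6.6% and 22.8% at an 80% event rate, and to between 5.9% and 12.7% at 50%. Even the 5-point gap exceeds 5% at both rates. The bias needs a gap between arms: a reader might infer that under-attribution alone inflates the error, but equal under-attribution costs power only.

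The stated sample size reproduces and is not in dispute. The point deserves correction because the ambiguity sits in the primary endpoint of an unblinded trial and the remedy is cheap.

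**What to change.** In 1.1.1, 13.1 and 13.4, use one definition: the proportion of patients with at least one grade 3-5 event of nausea/vomiting, ototoxicity, nephrotoxicity, neutropenia or thrombocytopenia within 90 days of starting chemoradiation, regardless of attribution. State that the list is exhaustive. Report the version restricted to events with possible, probable or definite attribution as a sensitivity analysis. In 13.2, say that the 80% and 50% rates refer to the all-cause count.

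The cost is wording only. The sample size stays as it is if 80% and 50% are all-event rates. The downside is that a few events not due to cisplatin enter both arms and slightly dilute the difference. The change does not remove unblinded judgment in grading clinical events such as nausea.

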1.1.2.1 Cohort 1: Unresectable locally advanced non-nasopharyngeal SCCHN

1.1.2.2 Cohort 2: Resected non-nasopharyngeal SCCHN at high risk of recurrence as defined by the following criteria:

- extracapsular nodal extension
- invasive cancer at the primary tumor resection margin (positive margin)
- lymphovascular invasion
- perineural invasion
- pT3 or pT4 primary
- presence of multilevel nodal disease

1.2 Secondary Objectives

1.2.1 To compare the following therapeutic endpoints in both populations:

- 2-year local control rates
- Overall survival (OS)
- Progression free survival (PFS)
- Response Rate (Cohort 1 only, as Cohort 2 is completely resected)

1.2.2 To compare and contrast the development of oxidative stress markers which occur as a result of exposure to weekly or every 3-week doses of cisplatin in this population

1.2.3 Rates of radiation related CTCAE adverse events, specifically: mucositis, dysphagia, dry mouth, and skin and their relationships with patient reported outcomes at 3 months and 12 months

1.2.4 CTCAE acute (< 90 days from start of chemoradiation) adverse events related (possibly, probably or definitely) to cisplatin or radiation

- 1.2.5 CTCAE late (> 90 days from start of chemoradiation) adverse events related (possibly, probably or definitely) to cisplatin or radiation.
- 1.2.6 Quality of life as measured by Functional Assessment of Cancer Therapy-Head & Neck (FACTHN) and Functional Assessment of Cancer Therapy Cognition (FACTCOG) at baseline, 3, and 12 months from end of RT

2. BACKGROUND

2.1 Squamous Cell Carcinoma of the Head and Neck Cancer (SCCHN)

SCCHN is a lethal disease that often presents in a locally advanced state. Surgery and radiation are the mainstays of treatment and provide a long-term survival of approximately 40-50% in inoperable subjects [1-3], and 40-60% in operable subjects [4-6], depending on stage and other risk factors, while 5-year PFS is often reported between 50 and 75% [2]. Defined criteria have evolved to delineate high-risk individuals in the postoperative setting: positive margins, lymphovascular or perineural invasion, extracapsular extension of lymph nodes, or multilevel nodal disease all increase the risk of local recurrence in this disease, a major cause of recurrence and death from SCCHN. Several biologic features predict sensitivity to cisplatin (HPV-driven cancer [7, 8], intact DNA repair mechanisms, and adequate renal and marrow function to allow full dose delivery); however a full understanding of individual sensitivity to cisplatin is needed to further refine the treatment of SCCHN.

2.2 Cisplatin in SCCHN

Concurrent chemoradiation using every 3-week cisplatin is the standard of care treatment for locally advanced (stage III and IV) squamous cell carcinoma of the head and neck (SCCHN). It is used as definitive treatment in inoperable patients and as adjuvant treatment after surgery in high risk patients [2-5, 8-18]. Multivariate analysis of over 16,000 patients (MACH-NC) revealed an overall survival benefit of 4.5% at 5 years in patients undergoing concomitant chemotherapy and radiotherapy, with platinum-based regimens significantly more effective than other types of chemotherapy. Multiple groups have published data regarding small randomized and nonrandomized trials comparing weekly versus every 3-weeks cisplatin but no large-scale phase 3 studies have been reported to date comparing lower to higher dose cisplatin delivery.

2.3 Oxidative Stress in Cancer

Reactive oxygen species (ROS) lead to oxidation of amino acid residue side chains, formation of protein-protein cross-linkages, and oxidation of the protein backbone resulting in inactivation of protein functions. As an example, HNE (a highly toxic form of ROS-induced lipid peroxidation products) may yield similar products and that heavy metal ions can promote formation of ·OH and O·⁻ in some of the reactions [19]. The ROS generated *in vivo* by some cancer therapies result in cancer cell killing, but also side effects in normal tissues. Toxic side effects of anti-cancer therapy lead to a loss of quality of life and acute and chronic damage to humans. Convincing mechanisms of action regarding normal tissue damage have been elucidated for the effect of

DNA damaging agents such as cisplatin, doxorubicin and others on normal tissues during human cancer treatment [20-25]. Critical to expanding this knowledge is the need for studies that focus on the generation of ROS or other markers of oxidative stress *immediately following* cisplatin infusion, and the degree of oxidative stress that occurs at various doses of cisplatin concurrent with radiation. Generation of ROS has been implicated in the toxicity of nearly 50% of the current FDA approved cancer therapeutic drugs. Formation of ROS is thought to lead to direct DNA damage by cisplatin via protein-protein cross-linkages and oxidation of the protein backbone resulting in inactivation of the protein function. The toxic side effects of cisplatin can lead not only to cognitive impairment, but renal, cutaneous, and other toxicities due to this phenomenon of ROS generation. While there is an understanding of high risk clinical features that predict survival in SCCHN, full knowledge of how an individual reacts to the oxidative stress caused by platinum compounds is not clear. This avenue of exploration will help to predict sensitivity to cisplatin, as well as to provide causative links to changes in cognition, toxicity and interaction with radiation. Further investigation of normal tissue response to injury resulting from drug-induced ROS generation and comparing ROS formation in response to various doses of platinum concurrent with radiation will provide an increased understanding of treatment response in SCCHN. This study is designed to gather that information, and to compare the efficacy of low and high dose cisplatin in the treatment of SCCHN, both in the inoperable and operable setting.

2.4 Tests to Assess Cognitive Function

Choosing an appropriate test for cognition is critical to be able to assess subtle changes in cognition as they occur in SCCHN. Well-established cognitive difficulties have been reported in other types of cancer, including breast and brain cancers [26, 27]. The FACTCOG [28] was chosen based on its reliability and validity, in addition to its demonstrated utility in assessing cognitive domains of interest in CICI, including attention and concentration, verbal and visual memory, and information processing speed as recommended by Vardy et al. and the Venice cognitive workshop [29, 30].

2.5 Overall Hypothesis

We hypothesize that weekly cisplatin will lead to a 1-year local control rate comparable to every 3-week (high dose) cisplatin in locally advanced SCCHN; however, there will be significantly fewer cisplatin-related acute toxicities for those treated weekly. We will also explore the relationship between cisplatin toxicity and the level of reactive oxygen species generated by the drug in subjects with squamous cell carcinoma of the head and neck treated on this trial.

3. PATIENT SELECTION

3.1 Eligibility Criteria

- 3.1.1 Patients must have pathologically (histologically or cytologically) proven diagnosis of head and neck squamous cell carcinoma (HNSCC) involving the oral cavity, oropharynx, larynx, hypopharynx, paranasal sinuses or unknown primary squamous carcinoma limited to the head and neck region;

- Cohort 1: Unresectable locally advanced non-nasopharyngeal SCCHN without evidence of distant metastases
- Cohort 2: Patients with non-nasopharyngeal SCCHN who have undergone gross total surgical resection within 63 days prior to registration. Patients must have at least 1 of the following high-risk pathologic features: extracapsular nodal extension, invasive cancer at the primary tumor resection margin (positive margin), lymphovascular invasion or perineural invasion, or the presence of multilevel nodal disease. Patients must be without evidence of distant metastases.

3.1.2 Women of childbearing potential and male participants who are sexually active must agree to use a medically effective means of birth control.

3.1.3 Cohort 1: Patients in Cohort 1 must have either (a) measurable disease, defined as at least one lesion that can be accurately measured in at least one dimension (longest diameter to be recorded for non-nodal lesions and short axis for nodal lesions) as ≥ 20 mm (≥ 2 cm) with conventional techniques or as ≥ 10 mm (≥ 1 cm) for non-nodal lesions, and > 15 mm (> 1.5 cm) for nodal lesions with spiral CT scan, MRI, or calipers by clinical exam or (b) evaluable disease based on evaluable non-target lesions (< 1.5 cm - > 1.0 cm) as specified in protocol section 11.1.1. See Section 11 for the evaluation of measurable disease.

Cohort 2: Subjects in the post-operative setting (Cohort 2) are not required to have measurable disease and response rate will not be assessed in cohort 2.

Date of resection: _____

3.1.4 Patients may have a history of prior head and neck malignancy, but must be able to tolerate full dose radiation and chemotherapy for the current head and neck cancer, as determined by the treating oncologist.

3.1.5 Age ≥ 18 years.

3.1.6 ECOG performance status 0, 1 or 2 (see Appendix A).

3.1.7 Life expectancy of greater than 12 weeks.

3.1.8 Patients must have normal organ and marrow function assessed within 14 days prior to registration as defined below:

- absolute neutrophil count $\geq 1,000/\text{mcL}$
- platelets $\geq 100,000/\text{mcL}$
- creatinine within normal institutional limits
- creatinine clearance $\geq 60 \text{ mL/min}/1.73 \text{ m}^2$ for patients with creatinine levels above institutional normal

OR

- 3.1.9 No prior chemotherapy for the **current** locally advanced SCCHN is allowed. Prior radiation or chemotherapy for a previous head and neck cancer is allowed provided full dose cisplatin and radiation can be delivered to the patient in this clinical trial and provided the patient is in remission from the prior head and neck cancer, and can undergo full dose radiation and chemotherapy for the current primary head and neck cancer.
- 3.1.10 Cisplatin and radiation are known teratogens. For this reason, women of child-bearing potential and men must agree to use adequate contraception (hormonal or barrier method of birth control; abstinence) prior to study entry, throughout the duration of active treatment and for 4 months after completion of chemotherapy and radiation. Should a woman become pregnant or suspect she is pregnant while she or her partner is participating in this study, she should inform her treating physician immediately. Men treated or enrolled on this protocol must also agree to use adequate contraception prior to the study, for the duration of active study treatment, and for 4 months after completion of chemotherapy and radiation (both induction and definitive) administration.

- 3.1.11 Ability to understand and the willingness to sign a written informed consent document.

3.2 **Exclusion Criteria**

- 3.2.1 Patients who have had chemotherapy or radiotherapy within 4 weeks (6 weeks for nitrosoureas or mitomycin C) prior to entering the study or those who have not recovered from adverse events due to agents administered more than 4 weeks earlier.
- 3.2.2 Patients who are receiving any other investigational agents.
- 3.2.3 History of allergic reactions attributed to compounds of similar chemical or biologic composition to cisplatin.
- 3.2.4 Patients with greater than grade 2 hearing loss.
- 3.2.5 No other prior malignancy is allowed except for the following: head and neck cancer in remission, adequately treated basal cell or squamous cell skin cancer, in situ cervical cancer, adequately treated previous Stage I or II cancer from which the patient is currently in complete remission or other cancer from which the patient has been disease-free for 2 years.
- 3.2.6 Patients with nasopharynx or salivary gland primary site.
- 3.2.7 Patients with distant metastatic disease (M1c) from the current head and neck cancer including brain metastasis.
- 3.2.8 Uncontrolled intercurrent illness including, but not limited to, ongoing or active infection (grade 3 or greater), symptomatic congestive heart failure, unstable angina pectoris, symptomatic cardiac arrhythmia, or psychiatric illness/social situations that would limit compliance with study requirements. Subjects with significant symptoms of congestive

heart failure who would not be expected to tolerate the IV hydration for cisplatin are excluded.

- 3.2.9 Pregnant women are excluded from this study because cisplatin and radiation are agents with the potential for teratogenic or abortifacient effects. Because there is an unknown but potential risk for adverse events in nursing infants secondary to treatment of the mother with cisplatin and radiation, breastfeeding should be discontinued if the mother is treated with cisplatin or radiation on this trial.
- 3.2.10 HIV-positive patients with uncontrolled HIV despite combination antiretroviral therapy are ineligible because of the potential for increased risk of lethal infections when treated with marrow-suppressive therapy. Appropriate studies will be undertaken in patients receiving combination antiretroviral therapy when indicated.

